5.5.9. Concomitant Therapy, Migraine Prevention Therapy, and Migraine Acute Treatment

For concomitant therapy summary, treatment group is based on (EM120, EM240, CM120, CM240)

The proportion of patients who received concomitant medication will be summarized for ITT patients for Study Period III and for the post-treatment population for Study Period IV separately. The concomitant therapy does not include migraine acute (abortive) treatments or migraine prevention therapy.

Concomitant therapies for study period III are those which started, stopped or continued in study period III. If medication started and stopped on the same day of injection, it will still be considered as concomitant medication for SP III. If medication started before the first day of injection but stopped on the same day of injection, then it will not be counted as concomitant medication for SP III.

Concomitant therapies for study period IV are those which either started, stopped or continued in Study Period IV. If medication started and stopped on the first day of SP IV, it will still be considered as concomitant medication for SP IV.

Treatment group comparisons will be done using the Fisher's exact test for Study Period III with ITT population. Descriptive statistics only will be presented for the treatment groups in Study Period IV with the post-treatment population.

Similar outputs for migraine prevention therapy will be created for SP III and SP IV. As mentioned in the previous section, the definition of the prevention therapy will be reviewed by medical before unblinding

Similar outputs for migraine acute treatment will be created for SP III and SP IV separately. The categorization is based on Section 5.5.8.

As mentioned in the previous section, the definition/categorization of the migraine prevention therapy and migraine acute treatments will be reviewed by medical before unblinding.

5.5.10. Efficacy Analyses

Table CGAP. 5.5 summarize the planned analysis for SP III, SP III and SP IV combined, and SP IV for efficacy analysis. All response rates are derived from migraine headache days unless otherwise specified. There will be no multiplicity adjustment for statistical test.

For summary of EM and CM patients, descriptive summary based on 6 arms (LY120/LY120, LY240/LY240, PLA/LY120, PLA/LY240, CM120, CM240) will be shown (SPIII and SPVI combined).

In addition, for CM patients, the statistical models such as MMRM or GLIMMIX will be used for some analysis with the treatment arm (CM120, CM240). In particular, only “number of MHD” analysis will be conducted by a statistical model (MMRM) as SP III and SP IV combined analysis. The other “analysis in SP III and SP IV combined” are by descriptive analysis.

Kaplan-Meier plot is based on 6 arms. The associated log-rank test is based on (CM120, CM240) only.

If analysis results would be considered less informative, then such results may not be provided in CSR.

Table CGAP. 5.5 Efficacy variables and Analysis Methods

Efficacy Variables	Analysis in SP III	Analysis in SP III/IV	Analysis in SP IV only
Number of MHD	MMRM	MMRM/ D	NA
Number of MHD with acute medication use	MMRM	D	NA
Number of MHD or headache days with acute medication use	MMRM	D	NA
Number of headache days	MMRM	D	NA
PGI-S	MMRM	D	NA

PGI-I	MMRM	D	NA
MSQ Total	MMRM	D	NA
MSQ Role Function-Restrictive domain	MMRM	D	NA
MSQ Role Function-Preventive domain	MMRM	D	NA
MSQ Emotional Function domain	MMRM	D	NA
MSQ each question summary	NA	D	NA
MIDAS Total (sum of item 1, 2, 3, 4, and 5)	MMRM	D	NA
MIDAS individual items (item 1, 2, 3, 4, 5, A, and B)	MMRM	D	NA
HCRU Summary	NA	D	NA
HCRU Migraine related events/100-patients-year	NA	D	NA
HCRU Employment status	NA	D	NA
PSMQ-M	NA	D	NA
PSMQ-M responder	NA	D	NA
X% response rate (X=50, 75, or 100)	GLIMMIX	D	NA
30% response rate	GLIMMIX	D	NA
Distribution of response rate (Month 12)	GLIMMIX/ D	NA	NA

Time from the end of SP III to no longer meeting 50% response criterion	NA	NA	KM/log-rank test
PGI-S responder (2 \geq improvement)	GLIMMIX/ D	NA	NA
MIDAS 50% responder	GLIMMIX/ D	NA	NA
MSQ Role Function-Restrictive responder (\geq 25 for EM or 17.14 for CM)	Logistic regression/ D	NA	NA

Abbreviation D: Descriptive summary based on 6 arms (LY120/LY120, LY240/LY240, PLA/LY120, PLA/LY240, CM120, CM240); GLIMMIX= generalized linear mixed model; KM= Kaplan-Meier plots; MIDAS = Migraine Disability Assessment test; MMRM = mixed-effects repeated measures analysis; MSQ (v2.1) = Migraine Specific Quality of Life Questionnaire version 2.1; PGI-I = Patient Global Impression of Improvement; PGI-S = Patient Global Impression of Severity;

Note 1: For MMRM, GLIMMIX, log-rank test, and logistic regression, analysis are based on 2 arms (CM120, CM240).

Note 2: Kaplan-Meier plots are based on 6 arms.

Continuous Efficacy Measures

For the continuous efficacy measures, the change from baseline to each post-baseline period will be estimated for each treatment from repeated measures analyses as described below, using PROC MIXED. When the objective is to assess overall mean change during the treatment phase, the endpoint will be estimated as the main effect of treatment from the MMRM analysis across Months 1-12 using Month 1 up to Month 12 data.

An MMRM analysis refers to a restricted maximum likelihood (REML)-based, mixed-effects repeated measures analysis using all the longitudinal observations at each post-baseline monthly visit. The MMRM models will include the fixed, categorical effects of treatment (CM120, CM240), month, and treatment-by-month interaction, as well as the continuous, fixed covariates of baseline value and baseline-by-month interaction.

An unstructured covariance structure will be used to model the within-patient errors. The Kenward-Roger (Kenward and Roger 1997) approximation will be used to estimate denominator degrees of freedom. If the model does not converge, the Fisher scoring algorithm will be implemented by specifying the SCORING option (SCORING=5) in SAS. If the model still fails

to converge, the model will be fit using covariance matrices of the following order specified by a decreasing number of covariance parameters until convergence is met:

- Heterogeneous Toeplitz = toeph
- Heterogeneous First-order autoregressive = arh(1)
- Toeplitz = toep
- First-order autoregressive = ar(1)

Hence we fit the model by the following order:

- [1] unstructured covariance with the default fitting,
- [2] unstructured covariate with the Fisher scoring,
- [3] toeph covariance with the default fitting,
- [4] toeph covariance with the Fisher scoring
- [5] arh(1) covariance with the default fitting,
- [6] arh(1) covariance with the Fisher scoring
- [7] toep covariance with the default fitting,
- [8] toep covariance with the Fisher scoring
- [9] ar(1) covariance with the default fitting,
- [10] ar(1) covariance with the Fisher scoring

When the unstructured covariance matrix is not utilized, the sandwich estimator (Diggle and Kenward 1994) will be used to estimate the standard errors of the fixed effects parameters. The sandwich estimator is implemented by specifying the EMPIRICAL option in SAS[®]. When the sandwich estimator is utilized, the Kenward-Roger approximation for denominator degrees of freedom cannot be used. Instead, the denominator degrees of freedom will be partitioned into between-subject and within-subject portions by the DDFM=BETWITHIN (DDFM=BW) option in SAS[®]. SAS[®] PROC MIXED will be used to perform the analysis. If the model is still non-convergence, then baseline-by-month interaction may be excluded from the model.

The analysis “Mean change from baseline (Visit 3) in the number of migraine headache days” result will be plotted by treatment arm (horizontal-axis= month, vertical-axis = change from baseline).

Binary Efficacy Measures

For the repeated binary efficacy measures such as responder indicators based on the number of migraine headache days, the visitwise binary responder indicators will be analyzed using a

categorical, pseudo-likelihood-based repeated measures analysis. This analysis will be implemented using the GLIMMIX procedure in SAS to compare treatments and include the fixed, categorical effects of treatment (CM120, CM240), month, and treatment-by-month interaction, as well as the continuous, fixed covariate of baseline value.

An unstructured covariance structure will be used to model the within-patient errors (denoted by TYPE=CHOL in the RANDOM statement). RESIDUAL option in RANDOM statement will be used to specify marginal model random effect. The Newton-Raphson method with ridging will be used for nonlinear optimization (denoted by including NLOPTIONS TECH=NRRIDG). The Kenward-Roger approximation will be used to estimate denominator degrees of freedom. If the model does not converge, the Fisher scoring algorithm will be utilized by the SCORING option in SAS (same as the MMRM models).

If the model still fails to converge, the model will be fit using covariance matrices in the following order (same as the MMRM models) specified by a decreasing number of covariance parameters until convergence is met:

- Heterogeneous Toeplitz = toeplitz
- Heterogeneous First-order autoregressive = arh(1)
- Toeplitz = toep
- First-order autoregressive = ar(1)

If necessary, both fitting algorithms will be used in the pre-specified order before proceeding to the next covariance structure in the sequence.

For models where the unstructured covariance matrix is not utilized, the sandwich estimator (Diggle et al. 1994) will be used to estimate the standard errors of the fixed effects parameters. The sandwich estimator is utilized by the EMPIRICAL option in SAS. When the sandwich estimator is utilized, the Kenward-Roger approximation for denominator degrees of freedom cannot be used. Instead, the denominator degrees of freedom will be partitioned into between-subject and within-subject portions by the DDFM=BETWITHIN option in SAS.

For the repeated binary secondary efficacy measures where the objective is to assess the proportion of patients with X% response during the first 6-month (or 12-month) treatment phase, the endpoint for comparing treatment arms will be estimated as the main effect of treatment from the categorical MMRM analysis across Months 1-12 using Month 1 up to Month 12 data.

Time to Event Measures

For the following time to event measures, a Kaplan-Meier curve of the time to event will be provided.

- Time to first loss of 50% response in post-treatment phase (SP III completer only)

It is calculated for patients who are Month 12 50% responders to the first month in Study Period IV at which these patients no longer meet the 50% response criteria. Patients who continue meeting the criteria until the end of the study will be censored.

Distribution of Response Rates

Overall x% response rate during the treatment phase will be estimated for X=0, 5, 10,..., 95, and 100, using descriptive summary and GLIMMIX model as described earlier in this section. These estimated response rates will be plotted and points within each treatment arm will be connected to show a curve of response rates. No statistical comparisons will be conducted among different treatment arms.

Analysis for PGI-S

Change from baseline in PGI-S scores will be analyzed.

PGI-S responder analysis will be conducted.

Analysis for PGI-I

The PGI-I raw value will be analyzed with a mixed model repeated measures analysis with PGI-S baseline score.

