4.2. Secondary Objectives

Table CGAP. 4.1 shows the secondary objectives and endpoints of the study. Table CGAP. 4.2 provides definitions for the terms referenced below.

Table CGAP. 4.1 Objectives and Endpoints

Objectives	Endpoints

Primary
 
To evaluate the long-term safety and tolerability of galcanezumab 120 mg/month or 240 mg/month in patients with migraine for 1 year of treatment.
	
Analysis of:
 
 • treatment-emergent adverse events (TEAEs) • discontinuation rates • vital signs and weight • electrocardiograms (ECGs) • laboratory measures • other safety parameters, including suicidality using the Columbia Suicide Severity Rating Scale (C-SSRS)

Secondary
 
 • To characterize the long-term pharmacokinetics, pharmacodynamics and immunogenicity of galcanezumab • To evaluate the long-term effectiveness of galcanezumab in the prevention of migraine 	
 • Assessment of serum concentrations of galcanezumab to enable a pharmacokinetic evaluation • Assessment of plasma concentrations of CGRP to enable a pharmacodynamic evaluation of target engagement of galcanezumab • Assessment of the development and consequences of ADA to galcanezumab in patients exposed to drug • Mean change from baseline (Visit 3) in the number of migraine headache days • Mean change from baseline in the number of headache days • Proportion of patients meeting 50% response criteria (reduction of at least 50% in the number of migraine headache days) • Mean change from baseline in PGI of illness as measured by PGI-S

Objectives	Endpoints

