
 • To evaluate the long-term effect of galcanezumab on quality of life • To evaluate patient satisfaction with medication • To evaluate safety and residual treatment effect during the post-treatment follow-up period 	
 • Patient’s global impression of improvement as measured by PGI-I • Mean change from baseline in the number of monthly migraine headache days requiring medication for the acute treatment of migraine headache • Mean change from baseline to endpoint in the evaluation of the MIDAS total score and individual items • Mean change from baseline to endpoint in the MSQ (v2.1) total score and individual domains • Descriptive summary at each visit for HCRU and employment status • Satisfaction with medication using the PSMQ-M • Analysis of safety parameters • Time to first loss of response (when patient no longer meets 50% response criteria) during the post-treatment follow-up phase

Abbreviations: ADA = anti-drug antibodies; CGRP = Calcitonin gene-related peptide; C-SSRS = Columbia Suicide Severity Rating Scale; ECGs = Electrocardiograms; HCRU = Health Care Resource Utilization; MIDAS = Migraine Disability Assessment test; MSQ (v2.1) = Migraine Specific Quality of Life Questionnaire version 2.1; PGI-I = Patient Global Impression of Improvement; PGI-S = Patient Global Impression of Severity; PSMQ-M = Patient Satisfaction with Medication Questionnaire-Modified; TEAEs = treatment-emergent adverse events.

Table CGAP. 4.2 Migraine and Headache Endpoint Definitions

Diagnosis	Definition/Criteria
Migraine headache (patients with EM only)	
A headache, with or without aura, of ≥ 30 minutes duration with both of the following required features (A and B):
 
A. At least 2 of the following headache characteristics:
 
 • Unilateral location • Pulsatile quality • Moderate or severe pain intensity • Aggravation by or causing avoidance of routine physical activity 
AND
 
B. During headache at least 1 of the following:
 
 • Nausea and/or vomiting • Photophobia and phonophobia 
(Definition adapted from the IHS ICHD-3 beta)

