5.5.3. Important Protocol Deviations

For protocol deviation summary, treatment group is based on (EM120, EM240, CM120, CM240, LY_ALL)

Listings of subjects with important protocol deviations will be provided for ITT population. The following list of important protocol deviations will be determined before DBL. Detail criteria and methods will be specified in a separate document which also specify exclusion of PPS/ITT/safety population.

- Violation of informed consent :(e.g. Lack of informed consent or late informed consent)
- Serious Adverse event not reported
- Deviation related to inclusion/exclusion criteria
- Deviation of the rescreen criteria
- Deviation of the operation of Visit
- Deviation of the discontinuation criteria
- Deviation of study treatment dosing
- Deviation of concomitant drug and therapy
- Other important protocol deviations as determined by the Lilly clinical/medical group

Summary of important protocol deviations will be made for

- Baseline and SP III
- SP IV

Listing of Important Protocol Deviations (include flags whether affected to PPS/ITT/safety or not) will be made for

- Baseline and SP III
- SP IV

It is based on 4 arms (EM120, EM240, CM120, CM240).

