5.5.8. Previous Migraine Prevention Therapy and Previous Migraine Acute Treatment

For previous migraine prevention therapy summary, treatment group is based on (EM120, EM240, CM120, CM240)

The proportion of patients who received previous migraine prevention therapy, and the proportion of patients with response to the previous migraine prevention therapy within each of

the 6 categories (to enter this trial, medical history event, adequate response, inadequate response, no response, and treatment availability) will be summarized for ITT patients. (Those reasons are captured at EM: CGAN Visit 1, CM: CGAP Visit 1). Treatment group comparisons will be done using the Fisher's exact test.

Previous migraine prevention therapies are migraine prevention therapies that started prior to the date of the first injection and stopped prior to or at the date of first injection (CGAN Visit 3 for EM patients, CGAP Visit 3 for CM patients) which has indication recorded in the CRF (prior therapy migraine medication, or concomitant medication) as one of the followings:

- [1] "Primary study condition" (except acute treatment)
- [2] Corresponding medical history event (preferred term) that includes "migraine" (except acute treatment)
- [3] Corresponding adverse event (preferred term) that includes "migraine" (except acute treatment)

Note that all records in the prior therapy migraine medication CRF have the indication "primary study condition".

Previous migraine prevention therapy and migraine prevention therapy during SP III and SP IV (Section 5.5.9) will be reviewed by medical to exclude non-migraine prevention therapy before DBL.

Previous migraine acute treatment during baseline (EM: CGAN Month 6, CM: SP II) will be summarized by following categories (can be multiple classes):

- triptans,
- NSAIDs/aspirin,
- acetaminophen/paracetamol,
- ergots,
- anti-nausea
- Chinese medicine
- Others

Previous migraine acute treatment are migraine acute treatment used in during the baseline. Migraine acute treatments will be identified by the concomitant medication CRF with one of the following indications:

- [1] "Primary study condition" (except migraine prevention therapies)
- [2] Corresponding medical history event (preferred term) that includes "migraine" (except migraine prevention therapies)
- [3] Corresponding adverse event (preferred term) that includes "migraine" (except migraine prevention therapies)

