Listing of Adverse Events Leading to Discontinuation and Serious Adverse Events (SP I, SP II, SP III, SP IV combined) will be created.

5.5.12.1.1.1. Potential Hypersensitivity events

Potential hypersensitivity events (immediate and no immediate) will be identified from a review of preferred terms generated from the following queries:

- Broad and narrow terms in the Anaphylactic reaction SMQ (20000021)
- Broad and narrow terms in the Angioedema SMQ (20000024)
- Broad and narrow terms in the Hypersensitivity SMQ(20000214)

Summary for the potential hypersensitivity events (SP III) will be created. These analyses will be medically reviewed to determine if the terms identified represent actual hypersensitivity events before DBL. Only those that are judged medically to be hypersensitivity events will be included in the tables of “hypersensitivity events”.

The number and percentage of patients with TEAEs (SP III) and AEs resulting in study drug discontinuation (SP III) will be summarized by treatment groups using MedDRA PT nested within the SMQ. Events will be ordered by decreasing frequency within the SMQ.

The number and percentage of patients with treatment-emergent hypersensitivity events by maximum severity (SP III) will be summarized by treatment groups using MedDRA PT.

The number and percentage of patients with TEAEs hypersensitivity events by timing (SP III) will be summarized using MedDRA PT nested within the SMQ. Events will be ordered by decreasing frequency. Note the timing of the hypersensitivity events is collected through eCRF and categorized into the following categories:

- During drug administration

- Within 30 minutes of end of study drug administration
- 30 minutes and up to 6 hours from end of study drug administration
- 6 hours and up to 24 hours from end of study drug administration
- 24 hours and up to 14 days from end of study drug administration
- Greater than 14 days from end of study drug administration

If these information was not collected, then such data will be excluded from the timing analysis.

The relationship between the development of treatment-emergent hypersensitivity events and TEAEs related to injection sites (SP III) will be summarized.

A listing of Subjects with Treatment-Emergent or Post-Treatment Emergent Potential Hypersensitivity Events will be created.

Figure of duration of Potential Hypersensitivity Events for each PT (SP III/IV) will be created.

5.5.12.1.1.2. Adverse Events Related to Injection Site

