5.8.2. Report to be Generated at Final Database Lock

For the final database lock, all TFLs will be created. At the timing of the final database lock, all randomized patients will have had a chance to complete or discontinue 12 months of treatment period (Study Period III) and 4 months of the post-treatment period (Study Period IV.)

Analyses at final lock combined with some of the analysis from interim analysis will be used in the final CSR.

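### SAP 5.5.10 allows results judged less informative to be left out of the CSR, with no criterion, decision-maker or timing, and ties the trigger to the results themselves

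*SAP*

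**What the plan says.** In its opening text, above Table CGAP. 5.5, SAP 5.5.10 says: "If analysis results would be considered less informative, then such results may not be provided in CSR".

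SAP 5.8.2 says of the final lock: "For the final database lock, all TFLs will be created". It continues: "Analyses at final lock combined with some of the analysis from interim analysis will be used in the final CSR".

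Three other places bear on what will be presented:
- SAP 5.5.1 says that the overall Month 1-12 estimate is to be shown for treatment comparisons at final lock, for the repeated PGI, MSQ, MIDAS and migraine-headache-day measures.
- SAP 5.5.10 and 5.5.11 say that the 6-arm descriptive summaries are to be shown.
- SAP 5.5.11 takes its quality-of-life methods and periods from Table CGAP. 5.5, but does not repeat the omission sentence.

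**The concern.** The condition for leaving a result out is a judgement about the result. As written, that judgement can be made after the result is known, by anyone, on any ground.

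Nothing else in the plan separates the decision from sight of the data. Dosing is unblinded from Visit 5. SAP 5.7 (Table CGAP. 5.9) has the project statistician, the medical staff and the medical writer unblinded no later than the CGAP interim lock, for CSR preparation among other purposes.

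At stake is the completeness of the secondary effectiveness results in the CSR. These include headline measures such as change in migraine headache days and 50% response, as well as the residual-effect endpoint "Time to first loss of response (when patient no longer meets 50% response criteria) during the post-treatment follow-up phase". A careful reader could find a missing analysis by comparing the CSR with Table CGAP. 5.5, but would not have its estimate. The CM dose comparisons are tested at two-sided 0.05 without multiplicity adjustment (SAP 5.5.1, 5.5.10), so the full set is needed to weigh any one nominal finding.

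**Working it through.** **Text check.** Both documents were searched for a definition of less informative, a named decision-maker and a time point for the decision. None was found. Set beside SAP 5.8.2, the sentence limits what the CSR reports and does not limit what is run.

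**What lies under the sentence** (counted from Table CGAP. 5.5 and Table CGAP. 4.1):
- Table CGAP. 5.5 has 25 rows. A 6-arm descriptive summary is planned for 20 rows in SP III/IV and for 4 more in SP III, which makes 24. The remaining row, time to loss of 50% response, has a 6-arm Kaplan-Meier plot.
- Rows with a CM120 versus CM240 comparison: 12 MMRM + 4 GLIMMIX + 1 logistic + 1 log-rank = 18. The response-rate distribution is not counted, because SAP 5.5.10 rules out comparisons for it.
- Comparisons, at one per variable and period: 11 single MMRM variables + 7 MIDAS items + 1 SP III/IV MMRM for migraine headache days + 6 GLIMMIX + 1 logistic + 1 log-rank = 27. Another counting rule would give another total.
- Secondary endpoints outside PK/PD, immunogenicity and safety: migraine headache days, headache days, 50% response, PGI-S, PGI-I, migraine headache days with acute medication, MIDAS, MSQ, HCRU/employment, PSMQ-M and time to first loss of response = 11.

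**Illustration for the CM dose comparisons.** The documents give no omission rate, so the shares below are assumptions. Suppose there is no dose difference and each test holds its nominal 5% level. The expected number with p<0.05 is 27 × 0.05 = 1.35, and the expected number without is 27 × 0.95 = 25.65.

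*Case A: omission unrelated to significance.* A share q is dropped from both groups, so the share of shown comparisons with p<0.05 is 0.05(1−q) / (1−q) = 5% for any q below 1.

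*Case B: only non-significant results are dropped.* The ratio of expected counts is 0.05 / [0.05 + 0.95(1−q)].

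| q (share of non-significant results dropped) | Shown with p<0.05 / all shown | Share |
|---|---|---|
| 0 | 1.35 / 27 | 5.0% |
| 0.5 | 1.35 / (1.35 + 12.825) = 1.35 / 14.175 | 9.5% |
| 0.8 | 1.35 / (1.35 + 5.13) = 1.35 / 6.48 | 20.8% |

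The percentages do not depend on the count of 27 or on independence between the tests. They do not apply to the 6-arm summaries, for which SAP 5.5.1 plans no comparison among arms.

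**The case against.** The best defence is that the sentence is housekeeping. The SAP's own text supports an innocent motive. The revision history explains that the 4-arm models were dropped because they did not handle the EM/CM baseline difference well, which is a reason of model adequacy. SAP 5.5.10 also prepares at length for non-convergence in models with about 30 CM patients per arm. On that reading, less informative means a poorly fitting or redundant table, and Case A applies. This stands as a plausible intent, but the wording is not limited to it.

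It can also be said that SAP 5.8.2 has final-lock analyses used in the CSR without promising that each one is presented, so the sentence need not break any rule of full presentation. That is fair. The gap is the missing criterion, whatever the default is taken to be.

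The SAP does fix timing for other judgements: "The following list of important protocol deviations will be determined before DBL"; prevention therapies "will be reviewed by medical to exclude non-migraine prevention therapy before DBL"; and, for hypersensitivity, "These analyses will be medically reviewed to determine if the terms identified represent actual hypersensitivity events before DBL". These concern classification of data and not choice of results to present. They show that the SAP fixes such judgements in advance elsewhere, but they do not make the omission sentence inconsistent.

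A reader might infer four stronger things that the documents do not support:
- *That unfavourable results were or will be left out.* Nothing shows this.
- *That the sentence was added after interim results were seen.* SAP Version 3 was written after preliminary interim results, but the documents do not say when this sentence entered.
- *That every secondary endpoint is certainly exposed.* The sentence sits in the efficacy section, its reach to quality of life is inferred from its place above the shared table and from SAP 5.5.11, and the statements that certain results are to be shown pull the other way.
- *That 9.5% or 20.8% estimates the actual distortion.* Those figures hold only if non-significance drives omission.

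**Conclusion.** The concern holds as a reporting gap of modest weight. The SAP permits results-dependent omission of secondary effectiveness results from the CSR without saying on what ground, by whom or when, and this sits uneasily with its own statements that certain summaries and comparisons are to be shown. The text finding is firm; the consequence is conditional. Under no dose difference and nominal 5% tests, the share of shown CM dose comparisons with p<0.05 ranges from 5% (omission unrelated to significance) to 9.5% or 20.8% (50% or 80% of the non-significant results alone omitted). No primary conclusion is touched, because the safety analyses in SAP 5.5.12 lie outside the sentence, and every output is still produced.

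**What to change.** Replace the sentence in SAP 5.5.10 with: *Every analysis in Table CGAP. 5.5 is reported in the CSR or its appendices; less informative results may be placed in an appendix.*

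This keeps the freedom to shorten the body of the CSR, removes the discretion to leave results out, states the reach to quality of life through the table, and settles the tension with the statements that results are to be shown. No new analysis is needed, because SAP 5.8.2 already has all outputs created. The cost is one sentence in the SAP and a slightly longer CSR appendix.

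The change should stop at the reporting rule. Requiring a between-arm estimate with a confidence interval for every comparison would be a separate matter and would add work, since the time-to-loss-of-response row has only a Kaplan-Meier plot and a log-rank test planned.
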